1.1: Nicotine deprived smokers will display selectively increased negative affect measured via startle potentiation during uncertain (vs. certain) threat relative to non-deprived smokers.

AIM 2: Examine the impact of stress neuroadaptation on negative affect, smoking urge, and smoking in response to stressors. Laboratory startle potentiation measures of stress neuroadaptation will predict ecological momentary assessment measures of:

2.1 ...overall levels of negative affect and urge
2.2 ...within-smoker covariation (i.e., coupling) of episodic stressors with negative affect, urge, and smoking (i.e., stressor-induced negative affect, urge and smoking).

AIM 3: Examine the impact of this stress neuroadaptation on smoking during the first two weeks of smoking cessation.

3.1: Laboratory startle potentiation measures of stress neuroadaptation will predict overall smoking during the first two weeks post-quit as well as measures of point prevalence abstinence and continuous abstinence measured at 2 weeks post-quit.

AIM 4: Determine if treatment of withdrawal via NRT reduces the influence of stress neuroadaptation.

4.1: Combo NRT with counseling (vs. placebo NRT with counseling) will reduce startle potentiation measures obtained at one week post-quit.

4.2: The effect of combo NRT (vs. placebo NRT with counseling) on smoking and related outcome measures will be mediated by change in startle potentiation measures from pre-quit to post-quit.

4.3: Treatment of withdrawal symptoms via combo NRT will attenuate the predictive strength of pre-quit startle potentiation measures with respect to overall levels of negative affect, urge, and smoking and stressor-induced negative affect, urge, and smoking.

RESEARCH DESIGN AND METHODS

C1: BRIEF OVERVIEW

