C2.4.1: Design Considerations and Justification: We discussed our careful considerations regarding our focus on the Cessation period and the use of this surrogate endpoint during a smoking cessation attempt in section A5 earlier. We also carefully considered an alternative design where we measured negative affective response during a single session of NRT administration to deprived smokers in the laboratory rather than at one week into a quit attempt. Although this alternative would be simpler, it may fail to capture a number of critical elements that are relevant to real-world quit attempts. In particular, the affective experience is likely quite different during a temporary deprivation period vs. a similar duration of deprivation in the context of an intended permanent cessation of use. Furthermore, the effects of deprivation likely vary over time during the cessation attempt as regulatory resources become drained and homeostatic adaptation processes are recruited (104,129–131). Our current design indexes negative affect both early in deprivation (during the pre-quit deprived session) and after one week of cessation. In addition, the 2 week quit period provides the opportunity for detailed real world measurement of stressor-affect, stressor-urge, and stressor-smoking relations via EMA (see below) that would not be available with the single NRT administration in the laboratory. We believe these benefits justify our current design.

Participants are instructed to continue NRT even if they fail to maintain complete abstinence during their quit attempt. There is evidence that participants benefit from reduced smoking on NRT even if full abstinence is not obtained or maintained (20). This procedure will allow all participants to be included in analyses of EMA cessation measures. Furthermore, analyses of the cued threat task that is administered at one week post-quit can retain all participants but include regressors/covariates to model the amount of smoking (and medication use) during the first week.

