During this visit, smokers will complete their second administration of the two NPU Task that was completed at their previous visit session. This assessment during combo NRT (or placebo) use will allow for tests of the effects of medication on our laboratory measures of negative affective response to uncertain threats. Furthermore, by measuring negative affective response to threats during medication use, we can now test if response on these tasks during medication use mediates smoking cessation outcomes associated with treatment of withdrawal symptoms via combo NRT.

C2.6.1: Design Considerations and Justification. We considered measuring cessation outcomes at later time points. However, the resources necessary to measure cigarette use after the EMA period has ended and/or to obtain biological confirmation of smoking status at later points was considered too large. As noted earlier, our primary focus is on the Cessation phase during the first 2 weeks. We expect the negative affective processes that are the focus of this application to have their greatest influence on cessation success during the first two weeks post-quit when withdrawal symptoms are most robust. Furthermore, smoking at later time points is expected to be increasing influenced by factors outside the focus of this application and therefore will display reduced relationships with our laboratory measures of negative affect. In addition, as the proportion of the sample that has relapsed increases with time since quit, power will be diminished to test our aims. For these reasons, we have focused our resources on this two week cessation period.

C3: EXPERIMENTAL CUED THREAT TASK

Building on basic affective neuroscience research with humans and animals reviewed earlier (30,31,62,75), we have developed and validated a laboratory task that is designed to measure negative affective response to threats broadly as well as selectively parse fear and anxiety. Consistent with current conceptualizations of fear and anxiety, the task presents participants with threats that are either certain or uncertain to assess their fear and anxiety, respectively. We manipulate uncertainty in the temporal domain by including conditions of imminent threat (shocks administered 5s post cue onset; certain threat) vs. distal/temporally uncertain threat (shocks administered anywhere post cue onset or during ITIs; uncertain threat). As per standard procedures in

[figure not shown]

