The Principal Investigator will refine existing protocols for assuring data accuracy and protocol compliance. Such protocols will include data verification and protocol compliance checks as well as other quality assurance procedures. The Principal Investigator will also be responsible for ensuring that the data for the project are securely stored, that storage is in compliance with University and federal regulations and that no unauthorized persons have access (electronic or physical) to any participant-identifiable data.

STATISTICAL CONSIDERATIONS

In this section, we outline general strategies for analysis of startle potentiation, EMA, and treatment outcome that are used to address our four aims. We sketch out clear exemplars of analysis options for this rich dataset. Of course, there are numerous supplemental analyses that space constraints prevent describing here.

ANALYSIS OF STARTLE POTENTIAION (AIM 1). The analysis of startle potentiation for Aims 1 & 1.1 across experimental tasks can be accomplished within very similar General Linear Models (GLMs). In each analysis, startle potentiation will be analyzed in a GLM with Threat Uncertainty (low vs. high probability for Threat Probability task; fixed vs. variable duration for Threat Duration task) as the focal within-subject factor.

Analysis of Aim 1.1 will use the full sample as a focal between-subject factor. Support for the stress neuroadaptation thesis following chronic tobacco use would be offered by a Smoking Group X Threat Uncertainty interaction with selectively greater startle potentiation among smokers in uncertain threat for each task. Analysis of Aim 1.2 will use both pre-quit sessions and include Deprivation Status (nicotine deprived vs. non-deprived) as a focal within subject factor. Support for the stress neuroadaptation thesis when nicotine deprived would be offered by a Deprivation Status X Threat Uncertainty interaction with selectively greater startle potentiation among deprived smokers in uncertain threat for each task.

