Additional covariates will be considered for each GLM to reduce error variance and increase power (e.g., resting startle response, task order, block order). All experiments include equal numbers of men and women to allow for preliminary examination of possible sex effects. Trait individual difference variables (e.g., individual differences in anxiety, depression, levels of tobacco dependence; see section C2.2) can be included in the GLMs to provide exploratory tests for potentially interesting moderators. Quantitatively measured withdrawal symptoms (WSWS) and smoking urge (QSU) can be included in supplemental analysis to clearly link deprivation status effects on startle potentiation to these proximal processes. Given that all participants complete both threat tasks, follow-up GLMs can include task as a within-subject factor to determine if effects are consistent across tasks that involve different manipulations of anxiety (i.e., low probability vs. temporally uncertain threat). This will provide important construct validation and potential conceptual replication of possible anxiety findings.

Analysis of Ecological Momentary Assessments of Stressors, Affect, Urge and Smoking (AIMS 2, and 4.3)

Analysis of EMA data will follow directly from procedures described by our Co-I, [name], in McCarthy, Piasecki, Fiore, & [name] (2006). Although the focal questions in McCarthy et al (2006) were different, the nature of that dataset was very similar in that it included multiple weeks of 4X daily EMA reports of stressors,

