Analysis of Treatment Outcome (AIMS 3, 4.1, 4.2): Number of cigarettes smoked (17,18), point prevalence abstinence and continuous abstinence (as defined by the SRNT Workgroup on Biochemical Confirmation (149)) will be analyzed in Generalized Linear Models with time (1 week vs. 2 weeks) as a within subject factor. Startle potentiation measures from the cued threat task will be included as quantitative regressors to test if our laboratory stress neuroadaptation biomarkers predict treatment outcome measures (Aim 3). As above, treatment condition can be included as a moderating between subject factor to test if the relationships between startle potentiation and treatment outcome differ generally when withdrawal symptoms. Finally, mediation analyses can be conducted to determine if NRT alters startle potentiation measures at one-week post quit (AIM 4.1) and the startle potentiation measures mediate NRT effects on smoking outcome measures (AIM 4.2).

C4.3: Sample Size Justification. The primary analyses of startle potentiation will be accomplished within the General Linear Model (GLM). The analyses of smokers test for a two way interaction between Deprivation Status and Threat Uncertainty. Cohen (150) defines 0.15 for the squared multiple partial correlation as a medium effect size for GLM analyses. To be conservative, we powered our experiments to provide 90% power to detect a somewhat smaller (0.10) effect size. N=142 will provide 90% power to detect a squared multiple partial correlation of 0.10 for the interaction in a model that contains the two main effects and interaction based on formula provided by Cohen. We then increased this sample size to the round 150 within each Treatment Group to provide flexibility to counterbalance all relevant additional task factors. This yields N=300 across the two Treatment Groups. Given that the multilevel models that will be used to test questions about the EMA data are essentially GLMs fit at two separate levels of analysis (occasion and person levels), N=150 within each Treatment Group will provide comparable high power to test person-level predictors of both occasion-level intercepts (e.g., overall smoking, levels of negative affect) and stressor coefficients (e.g., stress-instigated smoking or negative affect).

DATA AND RECORD KEEPING

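### Aim 4.1 has no specified model of post-quit startle by assigned arm, and the only covariates tied to that session arise after randomisation

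*Combined protocol and SAP*

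**What the plan says.** Under Specific Aims, Aim 4.1 is a comparison of arms: "Combo NRT with counseling (vs. placebo NRT with counseling) will reduce startle potentiation measures obtained at one week post-quit". The last paragraph of A5 gives the same purpose, and C2.6 says that the post-quit assessment "will allow for tests of the effects of medication on our laboratory measures of negative affective response to uncertain threats".

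The analysis text is thinner:

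- **Startle models (Analysis of Startle Potentiation, Aim 1).** Here "startle potentiation will be analyzed in a GLM with Threat Uncertainty" as the within-subject factor, together with smoking group and deprivation status. Treatment arm is absent. On covariates: "Additional covariates will be considered for each GLM to reduce error variance and increase power (e.g., resting startle response, task order, block order".
- **Analysis of Treatment Outcome (Aims 3, 4.1, 4.2).** The models written out have smoking outcomes as dependent variables and startle as a predictor. Arm enters as a moderator: "treatment condition can be included as a moderating between subject factor to test if the relationships between startle potentiation and treatment outcome differ". For Aim 4.1 itself, the text is "mediation analyses can be conducted to determine if NRT alters startle potentiation measures at one-week post quit (AIM 4.1".
- **EMA models.** Arm is again a moderator (Aim 4.3).
- **C2.2.** Screening questionnaires are available as covariates in general; no aim or session is named.
- **C2.4.1.** Analyses of the post-quit task "can retain all participants but include regressors/covariates to model the amount of smoking (and medication use) during the first week". This is the only covariate statement tied to that session.

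Aim 4.2 uses pre-quit startle, but only inside a mediator: the NRT effect on smoking is to be "mediated by change in startle potentiation measures from pre-quit to post-quit".

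**The concern.** Aim 4.1 is a question about assignment, and randomisation answers it if arms are compared as assigned. First-week smoking and medication use are both measured after randomisation. A5 cites an approximate doubling of long-term abstinence with NRT, C2.4.1 cites benefit from reduced smoking on NRT, and Aim 4.2 treats smoking as an outcome of NRT. The plan therefore expects one of these covariates to respond to treatment.

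Medication use has a further difficulty. EMA records patch wear and lozenge count (C2.5), but C2.4 makes these nicotine in one arm and placebo patches and mints in the other. A single common slope has no clear meaning.

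Because no main model is named, either an adjusted or an unadjusted coefficient could be reported as the Aim 4.1 result. The arm-to-startle effect is also the first link in the Aim 4.2 mediation claim.

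**Working it through.** **1. The plan's own figure.** C4.3 gives N=142 for 90% power at an effect size of 0.10. At an assumed two-sided 5% level, this reproduces with three numerator degrees of freedom and 0.10 read as f-squared: 14.17 / 0.10 = 141.7. (The exact noncentral F calculation gives 146.) It concerns the Deprivation Status by Threat Uncertainty interaction, so it neither supports nor contradicts a model for Aim 4.1. The only input taken from it below is 150 per arm.

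**2. Effect of adjusting for smoking.** Let d be the NRT reduction in first-week smoking (SD) and g the within-arm slope of post-quit startle on smoking, given session-1 startle. Then

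adjusted arm coefficient = as-assigned effect + d × g.

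The documents give neither d nor g. Assumed ranges are d 0.2 to 0.6 and g 0.1 to 0.3 in either direction. The last two columns assume an as-assigned effect of −0.30 SD.

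| d | size of g | size of shift | adjusted, g positive | adjusted, g negative |
|---|---|---|---|---|
| 0.2 | 0.1 | 0.02 | −0.28 | −0.32 |
| 0.4 | 0.2 | 0.08 | −0.22 | −0.38 |
| 0.6 | 0.3 | 0.18 | −0.12 | −0.48 |

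A simulation with 4000 trials per cell gives the same adjusted values, and as-assigned coefficients of −0.298 to −0.302. The shift agrees to within 0.003 whether smoking is a mediator or only shares a cause with startle. If d = 0 or g = 0, the shift is zero.

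**3. Scale.** The detectable difference is k × sqrt(2/150 × (1 − r²)), where r is the correlation between session-1 and post-quit startle (not given in the documents) and k is 3.24 for 90% power or 2.80 for 80%, two-sided 5% assumed.

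| r | 90% power | 80% power |
|---|---|---|
| 0 | 0.374 | 0.323 |
| 0.3 | 0.357 | 0.309 |
| 0.5 | 0.324 | 0.280 |
| 0.7 | 0.267 | 0.231 |

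At r = 0.5, shifts of 0.02, 0.08 and 0.18 are 6%, 25% and 56% of 0.324, or 7%, 29% and 64% of 0.280.

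**4. Effect of adjusting for medication use.** Assume that use lowers startle by 0.1 to 0.3 SD per SD of use in the active arm only. With equal arms the pooled slope is half that. If mean use differs between arms by 0.2 to 0.5 SD, the shift runs from 0.1/2 × 0.2 = 0.01 to 0.3/2 × 0.5 = 0.075 SD. It is nil if mean use is equal.

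**5. Precision from session-1 startle.** The standard error of the arm difference is sqrt(2/150 × (1 − r²)): 0.115 SD at r = 0, 0.110 at 0.3, 0.100 at 0.5 and 0.082 at 0.7.

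**6. Timing of the session.** Aim 4.1, C2.4.1 and the Analysis of Treatment Outcome put the task at one week post-quit. A5, C1, C2.3, C2.6, C3 and C3.3 put it at two weeks. At two weeks, a first-week covariate covers only half of the preceding period.

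**The case against.** The strongest reply is that C2.4.1 is permissive. It justifies keeping lapsers in the analysis, names neither Aim 4.1 nor an arm contrast, and describes a one-week session that may not be the one run. A reader might infer that the plan commits to adjusting the NRT effect for smoking and medication use; the documents do not say so. This stands, and it limits the point to what would follow if the offered covariates were used.

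The target is also clearer than the model. Specific Aims, A5 and C2.6 all express an arm effect on startle, C4.3 places the primary startle analyses in the general linear model, and any mediation model contains an arm-to-startle path. It would be wrong to say that Aim 4.1 has no analysis at all. But that path is never written out, given covariates or made the main estimate.

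Nor are these the only covariates in the plan: C2.2 and the Aim 1 section name others, though not for this session.

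It is tempting to say that the coefficient must move. It does not if the arms have the same smoking and product use, or if these variables are unrelated to startle within arm. The magnitudes above rest on chosen ranges and say nothing about what this trial will show.

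**Conclusion.** The point holds in conditional form and should be fixed. Aim 4.1 lacks a stated model of post-quit startle by assigned arm, and the only covariates tied to that session are ones that NRT may change. Using them would alter what the arm coefficient estimates if NRT changes them and they are related to startle.

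The illustrated shift is 0.02 to 0.18 SD for smoking and 0.01 to 0.075 SD for medication use. Every input except 150 per arm is assumed, and the documents fix neither direction nor size. A reader might infer a known bias for or against NRT; nothing in the plan supports that.

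The importance is moderate: Aim 4.1 is not the contrast behind the sample size, but it is a stated aim and the mediation claim depends on it.

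**What to change.** In C2.4.1 and the statistical section:

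1. State that the main Aim 4.1 estimate is post-quit startle potentiation by assigned arm, including everyone with a post-quit session regardless of smoking or medication use. Adjust for session-1 startle potentiation, which C2.3 places before medication is dispensed, and for block order.
2. Add randomised deprivation condition once it is confirmed that it is crossed with treatment arm. C2.3 ties the session-1 calendar to deprivation condition, while C2.4 refers to different visit calendars for the two arms. If the two were aligned, deprivation could not be separated from arm, and session-1 startle would not be a comparable baseline.
3. Label any model that adjusts for post-quit smoking, lozenge count or patch wear as exploratory or mediation, not as the NRT effect.
4. Reconcile the one-week and two-week statements of the task session, and match the window of any exploratory covariate to the session actually used.

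The cost is added text and slightly more analysis work, with no new data. The gain in precision depends on a between-session correlation that the documents do not give: the standard error falls from 0.115 to 0.100 SD at an assumed 0.5.
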